#### **7.4.4 STRUCTURAL MRI VISIT**

##### **sMRI Scan Visit (Visit 10)**

During the gap week between the 5th day of stimulation and the 1st maintenance session, we will ask the participant to come in and complete an sMRI scan. MRI scan imaging will take place at the Biomedical Research

Imaging Center (BRIC), located in Marsico Hall on the first floor. If the participant is a female of child-bearing potential, they will be asked to complete a urine pregnancy test prior to completing the scan. Screening questions asked prior to the MRI scan (*Attachment 8*) and all preparation for scans will take place in a facility area behind a locked door, where only research study personnel have access. When subjects are required to change their clothing, they will be allowed to do so alone, in a room with a door that locks. MRI scan will be performed by trained study personnel or designees of the PI that are approved to complete an MRI scan.

---

#### 7.4.5 MAINTENANCE SESSIONS

##### **Maintenance Stimulation Session Week 1 (Visit 11)**

Upon participant arrival, vital signs will be taken and documented. Female participants will complete a urine pregnancy test to rule-out pregnancy. An EEG will then be administered, with ECG data also being collected at this time. The EEG recording will include resting state data along with an auditory task, and the EEG Questionnaire will be administered. The participant will receive 40-minutes of sham or 10 Hz tACS (as per the randomization) while sitting quietly with their eyes open. The stimulation session will be followed by the stimulation adverse effects questionnaire. The AHRS and HPSVQ will then be administered to assess severity of auditory hallucinations. Participants will be paid at the conclusion of this study visit, and the next study visit will be scheduled for the following week.

##### **Maintenance Stimulation Session Week 2 (Visit 12)**

Upon participant arrival, vital signs will be taken and documented. Female participants will complete a urine pregnancy test to rule-out pregnancy. An EEG will then be administered, with ECG data also being collected at this time. The EEG recording will include resting state data along with an auditory task, and the EEG Questionnaire will be administered. The participant will receive 40-minutes of sham or 10 Hz tACS (as per the randomization) while sitting quietly with their eyes open. The stimulation session will be followed by the stimulation adverse effects questionnaire. The AHRS and HPSVQ will then be administered to assess severity of auditory hallucinations. Participants will be paid at the conclusion of this study visit, and the next study visit will be scheduled for the following week.

##### **Maintenance Stimulation Session Week 3 (Visit 13)**

Upon participant arrival, vital signs will be taken and documented. Female participants will complete a urine pregnancy test to rule-out pregnancy. The C-SSRS (follow-up version) will be administered next. If a participant answers 'yes' to items 3, 4, or 5 in the suicidal ideation section or answers 'yes' to any suicidal behavior since the week of stimulation, the study coordinator will call [name], who will determine if an acute assessment is needed. [name] will conduct this acute assessment if it is needed. An EEG will then be administered, with ECG data also being collected at this time. The EEG recording will include resting state data along with an auditory task, and the EEG Questionnaire will be administered. The participant will receive 40-minutes of sham or 10 Hz tACS (as per the randomization) while sitting quietly with their eyes open. The stimulation session will be followed by the stimulation adverse effects questionnaire. The AHRS and HPSVQ will then be administered to assess severity of auditory hallucinations. Participants will be paid at the conclusion of this study visit, and the next study visit will be scheduled for the following week.

##### **Maintenance Stimulation Session Week 4-7 (Visits 14-17)**

Upon participant arrival, vital signs will be taken and documented. Female participants will complete a urine pregnancy test to rule-out pregnancy. The participant will receive 40-minutes of sham or 10 Hz tACS (as per the randomization) while sitting quietly with their eyes open. The stimulation session will be followed by the

stimulation adverse effects questionnaire. The AHRS and HPSVQ will then be administered to assess severity of auditory hallucinations. Participants will be paid at the conclusion of this study visit, and the next study visit will be scheduled for the following week.

---

#### 7.4.6 FINAL STUDY VISIT

##### **Maintenance Stimulation Visit Week 8 (Visit 18)**

Upon participant arrival, vital signs will be taken and documented. Female participants will complete a urine pregnancy test to rule-out pregnancy. The C-SSRS (follow-up version) will be administered next. If a participant answers 'yes' to items 3, 4, or 5 in the suicidal ideation section or answers 'yes' to any suicidal behavior since the third week of maintenance, the study coordinator will call [name], who will determine if an acute assessment is needed. [name] will conduct this acute assessment if it is needed. An EEG will then be administered, with ECG data also being collected at this time. The EEG recording will include resting state data along with two auditory tasks, and the EEG Questionnaire will be administered. The participant will receive 40-minutes of sham or 10 Hz tACS (as per the randomization) while sitting quietly with their eyes open. After the session participants will complete the stimulation adverse effects questionnaire. The AHRS and HPSVQ will be administered to assess severity of auditory hallucinations, followed by the adverse events questionnaire and a review of current medications. The PANSS (*Attachment 5*), and BACS (*Attachment 6*) data collection assessments will be administered at the end of this session for endpoint assessment. Each participant will be asked whether they believe their symptoms have changed (better, worse, no change) over the course of the study. After the assessments are completed, the participant will then be paid for the completion of the final study visit.

---

#### 7.4.7 CASE STUDY

##### **Case Study**

A subset of participants (up to 4) will be recruited from the original participant pool for a 12-week case study evaluating the feasibility of long-term maintenance. Participants will self-identify as being interested, and the PI and CO-Is will then determine eligibility. Participants will receive 40-minutes of 10Hz tACS while sitting quietly with their eyes open, once per week for 12 weeks. Each stimulation will be followed by the stimulation adverse effects questionnaire and the AHRS and HPSVQ to assess severity of auditory hallucinations. Participants will not receive monetary compensation for the case study.

#### 7.4.8 SCHEDULE OF EVENTS TABLE

Procedures	Maintenance Stimulation (Week 8)	Maintenance Stimulation (Weeks 4 – 7)	Maintenance Stimulation (Week 3)	Maintenance Stimulation (Week 2)	Maintenance Stimulation (Week 1)	sMRI Visit				
eConsent REDCap	X									
Signed Consent Form		X								
SCID	X									
C-SSRS	X		X					X		X
Demographics	X									
Med History	X									
Medications	X-----X									
Handedness	X									
Beliefs about Tx	X									
BAS/BIS	X									
AHRS	X	X	X	X		X-----X				
HPSVQ	X	X	X	X		X-----X				
Vital Signs			X-----X			X-----X				
Pregnancy test			X		X	X-----X				
Urine Drug Screen			X							
PANSS			X	X						X
BACS			X	X						X
Randomization			X			X				
Stimulation			X	X	X	X-----X				
EEG			X	X		X		X		X
EEG Questionnaire			X	X		X		X		X
AE Interview			X-----X			X-----X				
Sx improvement Q's				X		X-----X				
sMRI					X					
HRV			X	X		X		X		X
Initial Visit via webex										

#### 7.5 PARTICIPANT ACCESS TO STUDY AGENT AT STUDY CLOSURE

We have included maintenance sessions in the study schedule in order to examine lasting effects of tACS. After the final maintenance session, no further treatment will be offered.

### 8 ASSESSMENT OF SAFETY

#### 8.1 SPECIFICATION OF SAFETY PARAMETERS

There will be three different assessments used to ensure participant safety. First, vitals will be recorded at the beginning of each session. This assessment is used to monitor any physiological changes.

A Positive and Negative Syndrome Scale will be administered before the first stimulation session and on the last day of stimulation as well as at the one month follow up. This tool is used to assess any changes in symptoms associated with this disorder. We do not expect any changes in these symptoms; additionally we did not find any changes in related clinical trials (IRB# 13-2995, IRB #14-3285). Should there be a significant change in PANSS rating scores, (>25% increase) we will direct the participant to [name] for further follow up and file a AE report.

The Columbia Suicide Severity Rating Scale will be administered at the initial session and roughly monthly intervals thereafter. The tool is used to assess recent and lifetime suicidality and will primarily determine if [name] should be called to conduct an acute assessment. Should a participant answer “yes” to items 3,4, or 5 on the Suicidal Ideation section or “yes” to any Suicidal Behavior question within a recent time period (specified above), [name] will be called to conduct an acute assessment and we will file an AE report.

After each stimulation session, a stimulation adverse effects questionnaire (*Attachment 1* and *Attachment 2*) will be administered. This tool is used to document any side effects experienced during stimulation. The researcher will also check with the participant throughout the 20 minute stimulation sessions to make certain no discomfort is felt. The stimulation session will be terminated if the participant reports having unmanageable discomfort or pain (more than “moderate”). Additionally, this information will be reported on an AE report form (*Appendix A*) and an AE log (*Appendix B*).

---

#### 8.1.1 DEFINITION OF ADVERSE EVENTS (AE)

**Adverse Event:** An AE, as defined by the NIH, is any unfavorable changes in health, including /abnormal laboratory findings that occur in trial participants during the clinical trial or within a specified period following the trial.

All AEs including local and systemic reactions not meeting the criteria for “serious adverse events” will be captured on the appropriate CRF. In addition, the AE Interview will be completed by the study coordinator during each lab visit (see attachment). For any Adverse events reported, a clinician will evaluate and indicate the severity of the event(s). The AE report form (*Appendix A*) will be completed for any reported AE. The AE form includes the following: what is known about the therapy and previous reported side effects, if the AE occurred in temporal relation to the therapy, whether or not the AE improves or disappears when treatment is stopped, whether the AE is a worsening of baseline symptoms or related to a concurrent medical condition or medication use. Once complete, both of these forms will be given to the PI and the Co-I who will review, comment and sign the forms. Completed forms will be placed in the participant’s folder.

The study coordinator will document any AE occurrence on the AE log (*Appendix B*) which includes information such as the date of the AE, severity, relationship to the treatment (assessed by the PI), actions taken, and outcome(s). The log will be reviewed and initialed by the PI 72 hours after being completed. All AEs occurring during the clinical trial will be documented appropriately regardless of relationship to tACS. All AEs will be followed to adequate resolution and will be graded for severity and relationship to the study treatment. Any medical condition noted at the initial session will be considered as baseline and not reported as an AE.

All AEs will be graded for severity using the following guidelines.

- **Asymptomatic:** the participant is exhibiting no symptoms due to the event; no treatment needed.
- **Mild** Adverse Event– Event results in mild or transient discomfort, not requiring intervention or treatment; does not limit or interfere with daily activities (e.g., insomnia, mild headache).
- **Moderate** Adverse Event – Event is sufficiently discomforting so as to limit or interfere with daily activities; may require interventional treatment (e.g., fever requiring antipyretic medication). In the case of a moderate adverse event the medical advisor may recommend an over the counter medication.
- **Severe and undesirable** Adverse Event – Event results in significant symptoms that prevents normal daily activities; may require hospitalization or invasive intervention (e.g., anemia resulting in blood transfusion).

Changes in the severity of an AE will be documented with the Note to File document (*Appendix G*) and will be filed in the participant's folder.

---

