#### 8.1.2 DEFINITION OF SERIOUS ADVERSE EVENTS (SAE)

**Serious Adverse Event (SAE):** An SAE, as defined by the NIH, consists of adverse events that result in death, require either inpatient hospitalization or the prolongation of hospitalization, are life-threatening, result in a persistent or significant disability/incapacity or result in congenital anomaly/birth defect. Other important medical events, based upon appropriate medical judgment, may also be considered Serious Adverse Events if a trial participant's health is at risk and intervention is required to prevent an outcome mentioned.

All SAEs will be recorded on the Serious Adverse Events Form (*Appendix C*), documented in the UE/SAE log and reported to the IRB. The SAE Form will be completed by the study coordinator, and includes information relating to the onset and nature of the SAE, relationship to the study treatment, seriousness of the SAE, treatment required as a response to the SAE, and outcome. This form will be filed in the participant's binder at the resolution of the event. The study coordinator will complete the UE/SAE log (*Appendix D*) which includes information such as the date of the event, time at which the study team was informed of the event, details, when the IRB has been notified, and the date that the SAE Form was completed.

---

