## APPENDIX A: AE REPORT FORM

### Adverse Effects Report:

*Reasons for Report (adverse event, time, date and place of occurrence if available):*

1. What do we already know about the therapy?
  - a.
2. What is the temporal relationship of the AE to the study therapy?
  - a.
3. Does the AE improve or disappear when the therapy is stopped?
  - a.
4. Is the AE a worsening of baseline symptom(s)?
  - a.
5. Is the AE a result of an underlying concurrent medical condition(s) or concurrent medication(s)?
  - a.
6. Additional Information provided by research team
  - a.

Research team member signature \_\_\_\_\_ Date \_\_\_\_\_

Co-Investigator :

---

---

---

---

Steps to be taken (if applicable)

---

---

---

---

CI signature \_\_\_\_\_ Date \_\_\_\_\_

PI Comments:

---

---

---

---

Steps to be taken (if applicable)

---

---

---

---

PI signature \_\_\_\_\_ Date \_\_\_\_\_

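### The baseline-condition rule in Section 8.1.1 has no exception for worsening and, read literally, conflicts with the protocol's own adverse-event text

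*Combined protocol and SAP*

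**What the plan says.** Section 8.1.1 closes its account of AE logging with a rule on pre-existing conditions: "Any medical condition noted at the initial session will be considered as baseline and not reported as an AE". No other passage qualifies it.

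The surrounding text points the other way:

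- Section 8.1.1 says an AE "is any unfavorable changes in health, including /abnormal laboratory findings that occur in trial participants during the clinical trial".
- The same section lists what the AE form must capture, including "whether the AE is a worsening of baseline symptoms or related to a concurrent medical condition or medication use". Item 4 of the form in Appendix A asks the same question.
- Section 8.1 gives a numeric rule: "Should there be a significant change in PANSS rating scores, (>25% increase) we will direct the participant to" a designated clinician "for further follow up and file a AE report".
- Section 8.1.2 builds the SAE category on the AE category. An SAE "consists of adverse events that result in death, require either inpatient hospitalization or the prolongation of hospitalization", or meets one of the other seriousness criteria. That section makes no exclusion for the disorder under study.

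**The concern.** Safety reporting depends on how an event is first classified. If a condition recorded at entry gets worse and the coordinator treats it as baseline, no AE form is opened and no severity grade is assigned. A hospitalisation for it need not reach the SAE form either, since an SAE must first be an AE.

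This matters here because every participant enters with schizophrenia or schizoaffective disorder and persistent hallucinations (Section 5.1), documented at the initial session by the SCID and the AHRS (Section 7.4.2). Worsening psychosis is a plausible harm in this population. Section 10.2 also removes anyone who discontinues early from the analysis. A participant who relapses and leaves therefore contributes nothing to the efficacy comparison, and the AE record becomes the main place where the harm could be seen.

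**Working it through.** The point is textual, apart from one interval. The plan states no figure to reproduce.

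**Step 1. Apply each passage to the same event:** a condition noted at the initial session worsens during the maintenance weeks.

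| Passage | Result for this event |
|---|---|
| 8.1.1, baseline rule, read literally | Not reported as an AE |
| 8.1.1, AE definition | An unfavourable change in health during the trial, so an AE |
| 8.1.1 and Appendix A item 4 | The form expects such events and asks about them |
| 8.1, PANSS rule | AE report if the rise exceeds 25% at a PANSS visit |
| 8.1.2 | SAE only if the event is an AE and meets a seriousness criterion |

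The first row conflicts with the next three, and the last row inherits whichever answer is chosen. The Appendix A item cannot settle the conflict alone, because the form is completed only once an AE has been reported.

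**Step 2. How far the PANSS rule reaches.** Sections 4.1.2 and 7.1 schedule the PANSS on stimulation day 1, on day 5 and at maintenance week 8. Section 8.1 also mentions a one-month follow-up, but Section 7.4 has no matching visit. Count the first stimulation day as day 0, so that the fifth is day 4, with weekday visits:

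- Maintenance starting the following week (Protocol Summary, Participant Duration): week 1 is days 7 to 11, and week 8 is days 7 + 49 = 56 to 11 + 49 = 60. The interval is 56 − 4 = 52 to 60 − 4 = 56 days.
- One gap week (Section 7.4.3, Day 5): add 7 days. Week 8 is days 63 to 67, and the interval is 59 to 63 days.

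The two statements of when maintenance starts need to be reconciled. Across both, the interval is 52 to 63 days. Section 7.4.6 places the week-8 PANSS at the end of the session, so all 8 maintenance stimulations come before it.

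**Step 3. What else operates in that interval.**

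- An AE interview is held at each lab visit (Section 8.1.1). It elicits events, but the baseline rule then bears on whether they are reported.
- The AHRS and HPSVQ are given at every maintenance session (Sections 7.4.5 and 7.4.6). The documents attach no AE threshold to either.
- The C-SSRS is repeated at maintenance weeks 3 and 8 (Sections 7.4.5 and 7.4.6) and has its own AE trigger (Section 8.1), but it measures suicidality.
- Section 2.3.1 provides a psychiatric referral when symptoms increase and does not mention an AE report.

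Between the two PANSS ratings, then, recording worsening psychosis as an AE rests on the interview and on how the coordinator reads the baseline sentence.

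**Step 4. Who is covered.** If medical condition includes the psychiatric diagnosis, the literal rule covers 40 of 40 planned participants, by Section 5.1. If it means somatic history only, it covers whatever such conditions are noted at entry, a number the documents do not give.

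**The case against.** The strongest reply is that a baseline is what later change is measured against. On that reading the sentence excludes the pre-existing condition itself and says nothing about its deterioration, which the AE definition already captures. The form item on worsening would be pointless otherwise, and the PANSS rule requires a report for worsening of the very disorder everyone has at entry. This is persuasive about intent, and it stands. It does not supply the missing exception: the sentence is the only rule on baseline conditions, and it is worded as an exclusion from reporting.

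A second reply is that medical condition may mean somatic history. The schedule table in Section 7.4.8 lists medical history separately from the SCID and AHRS, and Section 5.2 pairs medical or neurological illness with somatic examples. This is a fair reading, and the 40 of 40 figure depends on rejecting it. It would not remove the problem for worsening of a somatic condition recorded at entry.

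A third reply is that participants are seen weekly and asked about AEs each time. That is true and limits the practical risk, but the interview does not decide how a worsened baseline condition is classified.

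**Conclusion.** The point holds as a conflict between passages, of moderate severity. Applied literally, the baseline sentence could leave worsening of a recorded condition, psychosis included, out of AE reporting and so out of SAE reporting. The exposure is greatest over the 52 to 63 days between the last two PANSS ratings. This assumes a literal-minded coordinator and, for psychosis, that the sentence extends to the psychiatric diagnosis.

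Three stronger conclusions that a reader might draw are not supported:

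- **Worsening psychosis is never reported.** The text does not say so. The AE definition, the form and the PANSS rule all treat worsening as reportable, and Section 8.1.2 has no exclusion for the underlying disorder.
- **The DSMB sees only AE reports.** Section 8.4 sends it unexpected, suspected serious reactions within 24 or 48 hours, and Section 8.6 includes a stopping criterion based on cognitive scores.
- **The baseline must be moved to the first stimulation.** Counting from consent is a legitimate choice. Appendix A item 2 and Appendix C item 7 record timing relative to treatment, so onsets before treatment can be told apart.

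**What to change.** Reconcile the passages by extending the sentence in Section 8.1.1: a baseline condition that increases in severity or frequency, or that meets a seriousness criterion, during the study is recorded as an AE or SAE. This brings the rule into line with the AE definition, Appendix A item 4, the PANSS rule in Section 8.1 and the SAE definition in Section 8.1.2. It works whichever reading of medical condition is intended, and it leaves the start of the AE counting period where it is.

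The cost is one clause, a short briefing for coordinators and somewhat more AE forms. Visits, sample size and the efficacy analysis are unaffected.

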#### 8.1.2 DEFINITION OF SERIOUS ADVERSE EVENTS (SAE)

**Serious Adverse Event (SAE):** An SAE, as defined by the NIH, consists of adverse events that result in death, require either inpatient hospitalization or the prolongation of hospitalization, are life-threatening, result in a persistent or significant disability/incapacity or result in congenital anomaly/birth defect. Other important medical events, based upon appropriate medical judgment, may also be considered Serious Adverse Events if a trial participant's health is at risk and intervention is required to prevent an outcome mentioned.

All SAEs will be recorded on the Serious Adverse Events Form (*Appendix C*), documented in the UE/SAE log and reported to the IRB. The SAE Form will be completed by the study coordinator, and includes information relating to the onset and nature of the SAE, relationship to the study treatment, seriousness of the SAE, treatment required as a response to the SAE, and outcome. This form will be filed in the participant's binder at the resolution of the event. The study coordinator will complete the UE/SAE log (*Appendix D*) which includes information such as the date of the event, time at which the study team was informed of the event, details, when the IRB has been notified, and the date that the SAE Form was completed.

---

